Eligible but not randomly assigned patients. It is assumed that the BARI clinical trial results would hold true in a larger population of patients whose disease characteristics are similar to those of the BARI patients. To test this assumption, outcomes from the randomly assigned trial will also be studied in BARI-eligible patients who do not consent to random assignment. If after adjustments for differences between the randomly assigned and the eligible but not randomly assigned groups the long-term outcome by treatment is similar, then the trial results can be generalized to patients who meet BARI criteria.

In spite of careful statistical adjustments to maximize comparability, the investigation of end points among eligible but not randomly assigned patients will only have the status of a good observational study and will not be suitable for providing primary estimates for treatment comparisons. In particular, in the registry population treatment is recommended based on a variety of selection factors, many of which are subtle and cannot be measured. An additional problem to be solved in analyses of such data will be the definition and time of treatment assignment.

As is typical for observational studies, registry analyses will also explore and generate hypotheses regarding the relation of various patient characteristics to outcome (predictors of events). The characteristics to be considered will be the key baseline variables of the randomly assigned study. Periprocedural outcomes such as mortality, myocardial infarction, and other complications will serve as end points in these analyses; procedure-related complications and outcomes will in turn also serve as risk factors for long-term events.

Statistical methods such as linear regression, logistic regression, and Cox regression will be used to obtain adjusted estimates of the effect of prognostic variables on outcome. As in the trial, testing for qualitative interaction between treatments and risk may be appropriate.

Patients clinically but not angiographically eligible. A 5–10% random sample of patients who meet clinical criteria for the randomly assigned trial but are excluded on angiographic grounds will be used to assess the appropriateness of angiographic exclusion for BARI.

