In this sample baseline characteristics as well as in-hospital outcome and major follow-up events will be analyzed by the given treatment. Results of these analyses will lend insight into the prognostic importance of those vessel/lesion characteristics that are not otherwise present in BARI-eligible patients.

Determination of time 0. For the randomly assigned patients, the clear choice for time 0 is the time of random assignment. For registry patients, the time of assignment of the BARI identification number is used. Random assignment determines the treatment group in the clinical trial, but a clear-cut treatment assignment does not apply to registry patients. Here,

treatment can be defined by the management received within 2 weeks of BARI ID assignment, or alternatively within 3 months. The 2-week rule is based on the requirement that the assigned treatment be delivered within 2 weeks in the trial.

Quality Control/Reproducibility of Measurements

To establish the reproducibility of key measurements in BARI, replicate blinded assessments will be performed on randomly selected samples. Measures in this category include angiographic baseline characteristics, measure of PTCA outcome, occurrence of MI, cause of death, and functional test outcome. (Details for some of these analyses are described in the Central Laboratory sections located in Appendixes 6 and 7).

Reliability will be assessed by appropriate statistical techniques that are applicable to the replication of measurement design.

Exploratory Methods of End Point Analysis

Completeness of revascularization. With respect to CABG, it has been claimed that the more complete the revascularization the better the results. This clinically appealing statement has never been adequately tested because no one would randomly assign patients to complete versus incomplete revascularization. The BARI trial will indirectly test this hypothesis because the PTCA strategy does not necessarily aim for or achieve the completeness of revascularization that CABG does.

Percutaneous transluminal coronary angioplasty as a delay for coronary artery bypass graft surgery. An additional goal of BARI is to learn the rate and timing of the crossover from PTCA to CABG. A PTCA patient is a crossover case if he or she undergoes CABG at any time after random assignment either before or after PTCA. The percentage of patients who crossover, as well as the length of delay to CABG, will be analyzed.

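### Registry follow-up starts before the treatment group is known, so deaths before a procedure drop out of the registry PTCA and CABG groups but stay in the randomised arms

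*Protocol*

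**What the plan says.** All of this is in the Protocol, Data Analysis.

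- *Determination of time 0*, trial: "For the randomly assigned patients, the clear choice for time 0 is the time of random assignment". The Introduction to Data Analysis makes the primary analyses intention to treat.
- *Determination of time 0*, registry clock: "For registry patients, the time of assignment of the BARI identification number is used".
- *Determination of time 0*, registry groups: "treatment can be defined by the management received within 2 weeks of BARI ID assignment, or alternatively within 3 months". Only the shorter window is given a reason: "The 2-week rule is based on the requirement that the assigned treatment be delivered within 2 weeks in the trial".
- *Registry Analyses, Eligible but not randomly assigned patients*, use of the comparison: if, after adjustment, "the long-term outcome by treatment is similar, then the trial results can be generalized to patients who meet BARI criteria".
- The same subsection concedes two limits. Registry results "will only have the status of a good observational study and will not be suitable for providing primary estimates for treatment comparisons". And: "An additional problem to be solved in analyses of such data will be the definition and time of treatment assignment".

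The angiographically ineligible sample is also to be analysed by the treatment given. For the registry, the protocol states no landmark, no time-dependent treatment and no rule for deaths before a procedure.

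**The concern.** The clock starts at ID assignment, but the group label is earned later. To be labelled PTCA or CABG, a registry patient must live until the procedure. The time between ID and procedure is therefore death-free by construction in both procedure groups, and deaths in that interval go to a non-revascularised group or nowhere. In the randomised arms the same deaths count from randomisation in the assigned group.

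The two cohorts are then not like for like in the comparison that is meant to support generalisation. Registry mortality after each procedure is understated, more so where the wait is longer. Baseline adjustment by the regression models listed for the registry cannot put back deaths that the grouping rule has removed.

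**Working it through.** **Inputs from the protocol.** 5-year mortality of 5% under either strategy (Appendix 3). Windows of 14 days and 3 months, taken as 91 days (*Determination of time 0*).

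**Assumptions, because the protocol gives none.** No true difference between procedures. Exponential waits with means of 3 v 10 days (2-week rule) and 3 v 30 days (3-month rule), unrelated to risk. Hazard in the first 91 days equal to k times the protocol level, k = 1, 3, 5, 10.

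**The plan's own figure.** The registry text states none. The base rate comes from Appendix 3, whose calculation reproduces: SE = √(2 × 0.05 × 0.95 / 1200) = 0.0089, and Φ(0.025/0.0089 − 1.645) = 87.8%, against the stated 88%.

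**Step 1, hazard.** h = −ln(0.95)/5 = 0.01026 per year, which is 2.81 × 10⁻⁵ per day or about 0.085% per month.

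**Step 2, all deaths inside the window,** 1 − exp(−k·h·t):

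| k | 14 days | 91 days |
|---|---|---|
| 1 | 0.04% | 0.26% |
| 3 | 0.12% | 0.76% |
| 5 | 0.20% | 1.27% |
| 10 | 0.39% | 2.52% |

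**Step 3, the part lost from a procedure group.** Only deaths before the procedure are lost. For mean wait m and window L, the mean wait among those due within the window is m − L·e^(−L/m)/(1 − e^(−L/m)). This gives 2.87 and 5.42 days under the 2-week rule, and 3.00 and 25.40 days under the 3-month rule. The shortfall in a group's 5-year mortality, relative to counting everyone from time 0, is about k·h·(mean wait)·S₅. Here S₅ = exp{−h[91k + (1826.25 − 91)]} with h per day, which is 0.950, 0.945, 0.940 and 0.928 for the four k.

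Example, 3-month rule, k = 10, difference between procedures: 10 × 2.81 × 10⁻⁵ × (25.40 − 3.00) × 0.928 = 0.0058, or 0.58 point.

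Shortfall in percentage points:

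| k | 2 weeks: short wait | long wait | difference | 3 months: short wait | long wait | difference |
|---|---|---|---|---|---|---|
| 1 | 0.01 | 0.01 | <0.01 | 0.01 | 0.07 | 0.06 |
| 3 | 0.02 | 0.04 | 0.02 | 0.02 | 0.20 | 0.18 |
| 5 | 0.04 | 0.07 | 0.03 | 0.04 | 0.34 | 0.30 |
| 10 | 0.07 | 0.14 | 0.07 | 0.08 | 0.66 | 0.58 |

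The difference columns are the spurious contrast between procedures. The short-wait and long-wait columns are the gap between a registry group and a randomised arm with the same true mortality.

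**Step 4, simulation.** Four million patients per procedure under the same assumptions gave differences of at most 0.04 point under the 2-week rule, and 0.03, 0.17, 0.28 and 0.57 point under the 3-month rule. The Monte Carlo standard error is at least √(2 × 0.05 × 0.95 / 4,000,000) = 0.015 point, so the smallest values are close to noise and the two sets agree. Starting the clock at a landmark at the end of the window, among survivors, brought the difference to within 0.03 point of zero in every scenario.

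**Step 5, the non-revascularised group.** Under the 3-month rule with a mean wait of 30 days, about e^(−91/30) = 5% have no procedure due in the window, and the early deaths join them. Their simulated 5-year mortality was 6.3%, 9.3%, 12.2% and 18.6%, against a true 1 − S₅ of 5.0%, 5.5%, 6.0% and 7.2%. This takes everyone in that group to have been waiting for a procedure. Patients intended for medical care would dilute the distortion.

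**The case against.** **The wording is permissive and the analysis secondary.** The protocol says treatment can be defined in these ways, calls the timing of assignment a problem still to be solved, and gives the registry no primary role. Handling of pre-procedure deaths could sit in an analysis plan that is not at hand. This limits the weight of the point but does not remove it. The protocol fixes a clock and offers two grouping rules, and either one combined with that clock gives the bias. The limitation it explains is unmeasured selection, not survival to treatment. The transitional life table (*Repeat revascularization*) and the time-dependent covariates (*Cross-sectional and longitudinal analyses*) are proposed for the trial, not the registry.

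**A reader might infer a bias above 1 point and set it against the 2.5-point margin.** With pre-procedure mortality of 1% per month and waits of 8 v 2 weeks, (8 − 2)/4.345 × 1% = 1.38 points. The documents do not support this. A patient operated on at 4 to 8 weeks is not in the CABG group under the 2-week rule. Rates of 0.2% to 1% per month are about 2 to 12 times the protocol's 0.085%. At the protocol's rate, waits of 4 v 1 weeks and 8 v 2 weeks give only 0.06 and 0.12 point. The margin belongs to the randomised comparison. Some early excess risk is plausible, because the Glossary admits unstable angina or non-Q wave infarction stabilised for as little as 4 hours. But patients needing emergency revascularisation are excluded, and no early rate is given.

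**A reader might also infer that PTCA followed by CABG within the window would be labelled CABG.** The text does not say so. Since the protocol compares initial strategies, classification by first procedure is at least as natural.

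**Conclusion.** The point holds as a structural flaw in a secondary analysis. Under the stated clock and either window, registry procedure groups exclude deaths before the procedure and the randomised arms do not.

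The 2-week rule does little harm: a spurious difference between procedures below 0.1 point even at ten times the protocol's early hazard. The 3-month rule gives about 0.06 to 0.6 point over the range examined. Both favour the longer-wait procedure. The distortion is larger for any non-revascularised group, which matters most for the angiographically ineligible sample. All sizes depend on the assumed waits and early hazards.

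The documents do not support the conclusion that the primary result is affected, or that the registry comparison is made worthless.

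**What to change.** Amend *Determination of time 0* and the registry analysis text as follows.

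1. Name the 2-week window as the main definition and 3 months as a sensitivity analysis.
2. Classify by the first procedure received in the window, which also settles patients who have both.
3. Keep time 0 at ID assignment, but enter first procedure as a time-dependent covariate: untreated until the procedure, then PTCA or CABG. Pre-procedure deaths then count in untreated time, and periprocedural deaths, which the protocol makes a registry end point, stay with their procedure.
4. For this comparison only, analyse randomised patients in the same way. Label it observational and leave the intention-to-treat primary analysis unchanged.
5. Report pre-procedure deaths separately for each cohort.
6. Optionally add a landmark analysis at the end of the window in both cohorts as a sensitivity analysis. It omits early procedural deaths and conditions on survival, so those deaths must be shown beside it.

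The cost is analysis wording and some programming. *Scheduled Follow-up* says registry data match trial data apart from the early contact, lipid levels and treadmill tests, so no new collection of procedure or death dates should be needed. The change does not remove confounding by treatment selection, so the protocol's existing caveat should stay.

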PTCA should be performed in a cardiac catheterization laboratory that is capable of providing high-quality video images with immediate replay (including 4- or 5-in. image-intensifier modes), biplane imaging or rapidly available orthogonal single-plane images, compound angulated projections, hemodynamic monitoring, and high-quality film processing. A full range of commercially available guiding and dilating catheters and guide wires should be available. PTCA may be performed by either the brachial or femoral approach.

Each procedure begins with a coronary cine angiogram of the vessels to be dilated. At least two scout projections of each vessel are obtained. For each targeted lesion, PTCA is attempted with the goal of achieving <50% residual stenosis and normal **TIMI** (grade 3) distal flow*.² A PTCA procedure is considered completed when the patient is removed from the cath lab table.

Considerations of patient safety or logistics may require that the initial PTCA procedure be performed over more than one session. If this approach is used the decision to do so must be made by the end of the first procedure, and all subsequent procedures should be performed within 2 weeks after the first. After PTCA cine angiography of treated arteries should be repeated in the same projections as initially used. Additional projections may be acquired as needed.

Heparin should be continued for 24–48 hours after the procedure in patients whose PTCA was performed for total occlusion or was associated with lesion dissection, thrombosis, transient occlusion, or in whom distal embolization was observed. Oral calcium antagonist therapy should be continued for 4 weeks, and a regimen of one aspirin tablet per day should be indefinitely continued.

In the case of abrupt closure, every effort should be made to reestablish patency and flow and avoid MI. This effort may include emergency CABG or the use of *new technology devices*.

Complications

Patients are monitored for adverse events throughout the hospitalization. These complications and their definitions are listed in Appendix 5. The need for additional revascularization procedures, including emergency CABG and repeat PTCA for abrupt reclosure, are also recorded. Each lesion that is subjected to PTCA is assessed for the occurrence of dissection and acute closure.

Guidelines for Repeat Percutaneous Transluminal Coronary Angioplasty

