It is possible that patients who are randomly assigned to PTCA will have CABG before, during, or after their initial PTCA procedure. To ensure the appropriate use of CABG in such patients, the following guidelines are recommended. 1) Once the patient is randomly assigned, PTCA must be performed within 2 weeks to minimize the time during which pre-PTCA crossover could occur. 2) During the initial PTCA procedure, patients who experience closure of an artery that was previously patent but narrowed may require emergency CABG for relief of ischemia or infarction if they are refractory to repeat angioplasty or medical therapy. The decision to proceed with emergency CABG under this circumstance should be strictly based on the need to provide appropriate patient care. 3) After an initially successful PTCA, indications for subsequent elective CABG are either recurrence or persistence of disabling symptoms that are accompanied by evidence of myocardial ischemia resulting from inadequate or unsatisfactory PTCA and anatomy that is judged to be unsuitable for repeat PTCA. 4) Subsequent CABG may be necessary for the recurrence of symptoms and ischemia after a period of symptomatic relief with evidence of restenosis of a previously successfully dilated coronary artery, as described in the previous section. Patients who require revascularization after initial PTCA should first be considered candidates for repeat PTCA. PTCA may be repeated more than once if there is a repetitive recurrence of symptoms or severe ischemia as defined. The decision to proceed with CABG in such patients should be based on the presence of angina or ischemia of sufficient severity to warrant surgery in the presence of evi-

dence that the initial or repeat PTCA has been unsuccessful. If PTCA would be particularly difficult or associated with an increased risk of untoward events, CABG may be considered without repeat PTCA. 5) Subsequent CABG may be necessary for the recurrence of symptoms or ischemia resulting from the development of new CAD. Consideration should be given first to repeat PTCA. If repeat PTCA is judged to be inappropriate or not feasible, then CABG should be considered if the symptoms are disabling despite optimal medical therapy or if severe ischemia is documented.

Angioplasty Operator Certification

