Criteria for certification include participation as an independent operator in more than 300 elective PTCA procedures, of which at least 100 were multivessel disease cases; demonstration of a success rate per lesion of 85% or greater for subtotal lesions among the last 100 cases; overall incidence per patient of PTCA-related acute myocardial infarction or emergency CABG of 5% or less; and an overall mortality rate of 2% or less for elective PTCA patients.

To complete certification requirements, each BARI angioplasty operator submits to the Central Radiographic Laboratory (CRL) preprocedure and postprocedure films of five consecutive PTCA procedures performed on patients with multivessel disease. The Central Radiographic Laboratory evaluates the films and determines the quality of the procedures, requesting additional films as needed. In-depth information about the CRL may be found in Appendix F. The current BARI certified angioplasty operators at each participating clinical site are listed in Appendix 8.

Classification of Outcome of Percutaneous Transluminal Coronary Angioplasty

To define what constitutes a successful PTCA procedure is complex. One approach will be to assess lesion improvement. The following are requirements for complete lesion improvement: TIMI grade 3 flow, luminal diameter reduced by $\geq 20\%$, and residual stenosis of $< 50\%$ diameter narrowing. If partial, the lesion that is subjected to PTCA has all of the following features: TIMI grade 3 flow and luminal diameter reduced by $\geq 20\%$ but residual stenosis of not $< 50\%$ diameter narrowing. If there is no lesion improvement, neither of the above definitions for this improvement has been met.

Patients who undergo a PTCA procedure in which each diseased vessel is not dilated but all targeted vessels are improved is classified as "incompletely revascularized by intent." Patients in whom PTCA results are partially satisfactory (that is, not all targeted vessels are improved) are classified as "incompletely revascularized but not by intent."

Lesion Classification

In the analysis of PTCA outcome, it will be important to describe the characteristics of the lesions that

are targeted for treatment. The lesion classification system developed for use in BARI is described below.

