Repeat revascularization. The attribution of events in the presence of subsequent revascularization by a treatment other than the one randomly assigned is of particular concern in BARI. Although the literature has described many avenues of analysis in such situations, none of these analyses can be interpreted in a classical statistical sense. However, to assess the impact of crossover two ancillary methods of analysis are proposed, with the clear understanding that the results obtained must be interpreted in the same manner as any other observational study results.

The first exploratory method is to censor follow-up at the time of the different method of revascularization. This approach looks at patients only during the continuation of their originally assigned treatment and does not count events after initiation of the other treatment. This method of analysis has less power to detect differences between the treatment groups because many patients may be lost because of a subsequent procedure. More importantly, this method could also lead to biased results if subse-

quent procedures occur frequently and in a highly selective manner, removing individuals who are either at more or less risk than others for the end point of interest. This possibility must be examined before such analysis, and great care should be exercised in drawing inferences.

A second auxiliary method is the transitional life table analysis, in which patients are considered to be members of their original treatment group until the different revascularization procedures and members of the other group thereafter. This approach allows all follow-up data to be used in the analysis, although there may again be bias because patients who subsequently receive the other treatment may be different from those who remain with their treatment assignment.⁴

These two methods have been useful in previous studies.⁴

Organizational Structure

Introduction

Investigators in the BARI study collaborate through an organizational structure designed to maintain the continuity of study operations and to facilitate effective communication and cooperation among components.

Operational Components

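### The two exploratory crossover analyses treat emergency CABG for a failed initial PTCA as an ordinary switch, so deaths after it are left out or booked to CABG

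*Protocol*

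**What the plan says.** In the Protocol's Data Analysis chapter, under Exploratory Methods of End Point Analysis, the paragraph on PTCA as a delay for CABG defines crossover: "A PTCA patient is a crossover case if he or she undergoes CABG at any time after random assignment either before or after PTCA". Urgency and reason play no part in this definition.

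The paragraph on repeat revascularization then proposes two ancillary analyses. "The first exploratory method is to censor follow-up at the time of the different method of revascularization"; this approach "does not count events after initiation of the other treatment". The second is the transitional life table, in which "patients are considered to be members of their original treatment group until the different revascularization procedures and members of the other group thereafter". Neither rule has an exception or a lag for an operation done to rescue a failed PTCA.

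Elsewhere the Protocol expects such operations. On abrupt closure, the guidelines for the PTCA procedure say of the attempt to restore flow: "This effort may include emergency CABG or the use of" new devices. Item 2 of the guidelines for subsequent CABG says that, during the initial PTCA, "patients who experience closure of an artery that was previously patent but narrowed may require emergency CABG for relief of ischemia or infarction". The introduction to Data Analysis says that the trial compares strategies and not the procedures as such, and it makes intention to treat the basis of every primary analysis.

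**The concern.** Take a patient assigned to PTCA whose artery closes on the table, who goes straight to emergency CABG and dies. The censoring analysis ends this patient's follow-up at the operation, so the death never appears. The transitional life table moves the patient to the CABG group at the operation, so the death counts against CABG. In both cases a bad outcome of the assigned PTCA leaves the PTCA group because surgery was the last rescue tried. This fits poorly with a comparison of strategies, since the Protocol's own PTCA guidelines list that surgery among the responses to closure.

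At stake is how two exploratory results would be read. They are the analyses that the Protocol offers to show the impact of crossover, and the paragraph that introduces them says that attribution of events is its main worry.

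**Working it through.** **The plan's own figure, for scale.** The Sample Size appendix takes 1,200 patients per arm, 5% mortality at 5 years in both arms and a limit of 2.5 points, and states a probability of 88%. SE = √(2 × 0.05 × 0.95 / 1,200) = 0.0089. Then Φ(0.025/0.0089 − 1.645) = 87.8%, which reproduces the 88% with a one-sided 5% limit. The appendix's 5% and 1,200 are used below.

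**Inputs not in the documents.** No rate of emergency CABG in the trial, and no mortality after it, is given. I assume a rate e of 1–5% and an acute mortality q of 2–15%. The upper value of e is only a bound. The operator certification criterion is an "overall incidence per patient of PTCA-related acute myocardial infarction or emergency CABG of 5% or less", so it also counts infarction and describes an operator's past record.

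**Direction.** These patients "may require emergency CABG for relief of ischemia or infarction if they are refractory to repeat angioplasty or medical therapy". Higher mortality than in other PTCA patients is plausible, but the documents do not quantify it.

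**Expected values with no other crossover.** Let true mortality be 5% in both arms, with emergency CABG at about time zero. Let b be the 5-year mortality of PTCA patients without emergency CABG and of those who survive its acute phase.

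- b = (0.05 − eq) / (1 − eq)
- Mortality after emergency CABG: m = q + (1 − q)b
- Censoring: PTCA shows b, CABG shows 0.05
- Transitional: PTCA shows b, CABG shows (0.05 + e·m) / (1 + e)

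For e = 2% and q = 10%: b = 0.048/0.998 = 4.81%; m = 0.10 + 0.90 × 0.0481 = 14.33%; transitional CABG = (0.05 + 0.02 × 0.1433)/1.02 = 5.18%. The acute deaths number 1,200 × 0.02 × 0.10 = 2.4.

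| e | q | Acute deaths | PTCA, both methods | CABG, transitional | Censoring difference (points) | Transitional difference (points) |
|---|---|---|---|---|---|---|
| 1% | 2% | 0.2 | 4.98% | 5.02% | −0.02 | −0.04 |
| 2% | 5% | 1.2 | 4.90% | 5.09% | −0.10 | −0.19 |
| 2% | 10% | 2.4 | 4.81% | 5.18% | −0.19 | −0.37 |
| 5% | 10% | 6.0 | 4.52% | 5.43% | −0.48 | −0.91 |
| 5% | 15% | 9.0 | 4.28% | 5.65% | −0.72 | −1.37 |

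Differences are PTCA minus CABG, and the true value is 0. Keeping these patients in the PTCA group restores 5% against 5%, but only because this set-up has no other crossover.

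**With later crossover added.** I simulated 400,000 patients per arm with 25% late elective CABG in the PTCA arm (an assumption). Monte Carlo error of a difference is about √(2 × 0.05 × 0.95 / 400,000) = 0.05 points. Entries are PTCA minus CABG in points, first under the stated rule and then with emergency CABG kept in PTCA.

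| Case | Intention to treat | Censoring | Transitional |
|---|---|---|---|
| e 5%, q 10%, 2% operative death at late CABG | 0.92 | 0.02 → 0.50 | −0.80 → 0.13 |
| e 2%, q 10%, same | 0.66 | 0.02 → 0.22 | −0.58 → −0.18 |
| e 2%, q 0%, same | 0.48 | 0.00 → 0.01 | −0.41 → −0.41 |
| e 2%, q 10%, no operative death, hazard halved after crossover | −0.11 | 0.04 → 0.19 | 0.14 → 0.45 |

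The emergency component moves both results towards PTCA whenever q is above zero, and it vanishes when q is zero. In the last case the analyses as written put PTCA slightly worse than intention to treat, so the component does not fix the net direction.

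**The case against.** The strongest reply is that the Protocol has already limited these analyses. It calls them ancillary, says that they cannot be interpreted in the classical sense, and asks for them to be read as observational results. For censoring, it warns that the people removed may be at higher or lower risk and requires this to be examined first. For the transitional method, it warns that switchers may differ. It also keeps the harm visible elsewhere: emergency CABG is recorded after PTCA, procedural complications are reported by treatment group to the monitoring board, and a death within 30 days of PTCA needs a catheterisation report for classification. Detail on urgency could also be left to a statistical analysis plan.

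Most of this stands as a limit on importance, but it does not remove the point. The warnings concern who switches. They do not address the booking of a death after failed PTCA to the rescue procedure. The Protocol also states a definite rule, and an analyst who follows it will code these deaths in the way described.

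Four stronger readings are tempting, and the documents do not support them:

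- That the trial's main conclusion is exposed. It rests on intention to treat, and the 2.5-point limit belongs to that comparison.
- That the two analyses as a whole must flatter PTCA. Late elective CABG and switches from CABG to PTCA also enter, and the net sign depends on them.
- That all deaths from PTCA complications are moved. Deaths without a CABG stay with PTCA.
- That the delay-to-CABG result is spoiled. That paragraph asks for the rate and timing of crossover, and day-0 operations are part of the timing. Showing them separately is a reporting choice.

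**Conclusion.** The point holds for the two exploratory crossover analyses only. As written, a death after emergency CABG for a failed or complicated initial PTCA is uncounted under censoring and counted against CABG in the transitional life table. This component favours PTCA if mortality after emergency CABG exceeds that of other PTCA patients. With equal true mortality of 5%, emergency CABG in 1–5% and acute mortality of 2–15%, it is worth about 0.02–0.7 points (censoring) and 0.04–1.4 points (transitional). At 2% and 10% it is about 0.2 and 0.4 points. These rates are assumptions, and the upper ends combine a ceiling that also counts infarction with the highest assumed mortality. The reading of the rule is firm; the size is not. It is a modest correction to secondary results.

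**What to change.** In the paragraph on repeat revascularization, state that emergency CABG for a failed or complicated initial PTCA triggers neither censoring nor switching, so that the operation and the deaths that follow it stay in the PTCA group. Apply the mirror rule to emergency PTCA for a complication of the initial CABG.

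Show both ancillary analyses with and without this rule. The pair is needed because keeping these patients in the PTCA group also credits PTCA with their later outcome on grafts, which is a misattribution in the other direction. For the same reason the rule should be limited to emergency operations and should not take in every CABG within a fixed number of days.

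The cost is small: a change of analysis wording, slightly fewer switch events and one extra set of exploratory results. The Protocol already has emergency CABG after PTCA recorded and requires forms for every subsequent revascularization. Patient management does not change.
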